- (i) (a) **HIV testing** and (b) SRH-related prevention services uptake among adolescent girls aged 16-19 in up to 9 intervention schools (with enhanced HIVST, PrEP, and contraceptive method offerings) compared to up to 9 control schools using a quasi-experimental difference-in-difference approach; and
- (ii) **linkage to care and treatment, and viral load suppression and retention at 6, 12, and 24 months** through a cohort model using pre-existing SmartCare data on HIV+ individuals in care to match to adolescent girls aged 16 and over from the same district (Lusaka) who are identified to be HIV+ at any time during SKILLZ Girl or SKILLZ Club participation and enrolled in SKILLZ-Plus.

This will be achieved by i) using a quasi-experimental difference-in-difference approach that compares girls aged 16 and over in 9 SKILLZ control schools compared to 9 schools where enhanced SKILLZ will be delivered with the enhanced HIVST and a variety of contraceptive method offerings; and ii) through a cohort model using pre-existing SmartCare data on HIV+ individuals in care to match to adolescent girls aged 16 and over from the same district (Lusaka) who are identified to be HIV+ at any time during SKILLZ-Girl or SKILLZ-Club participation.

Aim 2: Examine how the intervention works including lessons learned for future implementation by

- (i) conducting a process evaluation to identify mediators, predictors, and barriers to uptake of the SKILLZ-Girl, Club, and Plus curricula both quantitatively through mediation and moderation analyses and qualitatively through a sequential explanatory approach using focus groups discussions, interviews and observation with coaches and girls; and by
- (ii) monitoring fidelity

Aim 3: Estimate the short- and long-term cost-effectiveness and return on investment of the SKILLZ Girl, Club, and Plus curricula for improving health outcomes for adolescent girls.

8. Methodology

a. Study design

We will conduct a mixed-methods evaluation of the SKILLZ intervention using the following approaches:

A **quasi-experimental cohort** of school-aged 16-year old and over females to be followed for a two-year period will be evaluated with a difference-in-difference (DID) approach to estimate HIV testing uptake and sexual/reproductive health services use. Primary and secondary outcomes will be measured at several

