timepoints longitudinally across up to 9 schools offering the enhanced SKILLZ-Girl and SKILLZ-Clubs program and up to 9 schools offering the “standard of care” (SOC) SKILLZ-Girl and SOC Clubs (see Figure 3). Recruitment will take 12 months on a rolling basis. The order in which schools will be selected will be random. Participants will be clustered at the school-level; we will enroll all girls aged 16-years at the commencement of SKILLZ-Girl and in Grade 10 from each participating school.

[figure not shown]
All enrolled girls will be followed over the two-year time period to assess SRH service uptake, including HIV testing. It is estimated that the majority (~98%) of girls testing for HIV will likely be HIV-negative, based on estimates from programmatic GRS data. While HIV-positive girls will continue to participate in the school-based SKILLZ-Girl and Clubs activities and followed for SRH use, they will also be offered contemporaneous enrollment into SKILLZ-Plus upon infection; retention in care and Viral Load Suppression (VLS) at 6, 12, and 24 months will be measured for this subset. See **Figure 2** for details of enrolment flow.

Process evaluation: We will conduct a process evaluation to better understand the casual pathways and effect mediators and moderators using mixed methods approaches, including supplemental qualitative data collection. To investigate reasons why the program components (SKILLZ-Girl, Club & Plus) might fail or succeed in different schools or communities and assess intervention effect mediators and moderators for HIV testing and contraceptive use uptake we will use a mixed methods approach involving: (1) quantitative analyses of baseline survey data for testing how variables can moderate the observed impact of the intervention, and (2) qualitative data collected from a subset of SKILLZ participants in the evaluation cohort and their coaches to further understand potential mediating pathways outlined in Figure 1.

Fidelity monitoring: We will also include measures to monitor fidelity of the intervention implementation, including receptivity to and understanding of the intervention amongst participants, the perceived appropriateness and relevancy of the intervention for adolescent girls in school, and the extent to which the intervention was delivered per protocol in different communities and schools.

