Economic evaluation: We will estimate the short- and long-term cost-effectiveness and return on investment of SKILLZ for improving health outcomes for adolescent girls.

Figure 2. Evaluation enrolment flow

b. Study site and population/Research materials

Lusaka is the capital and the most inhabited city in Zambia. Home to 2 million people, it has the highest HIV prevalence at 14%⁴. The study will take place across all the highly densely populated areas of Lusaka where

[figure not shown]
CIDRZ supports government MoH clinics with ARV services, electronic data management, and youth-friendly trained clinical personnel, and where GRS has been implementing their basic curriculum and events. All schools selected will be secular government schools. Approximately 80% of school-age girls are reported to be in school in Lusaka. To facilitate the evaluation of SKILLZ, all girls enrolled in up to 18 government secondary schools in Urban Lusaka that GRS currently serves will be eligible to participate in the SKILLZ program and will be randomly allocated to either the enhanced or SOC SKILLZ implementation. For measuring impact, only girls aged 16 and over enrolled in Grade 10 at the start of the intervention period will be surveyed and followed because youth aged 16 and over can consent for SRH/HIV services without additional parental permission⁵⁵. (See *Section 9: Ethical Considerations* for details on waiver of parental consent).

c. Selection of participants, sampling methods and sample size

Study Population: In each school, we will recruit all girls in Grade 10 who are at least 16 years old at the start of the intervention period (i.e., the commencement of SKILLZ-Girl). Of the 30,000 youth in Lusaka that have benefitted from GRS services to date, GRS has seen HIV testing uptake of 62% as compared to a baseline of 13% (internal program data). We have powered the sample for our primary endpoints in Aim 1ii to account for attrition anticipated along the cascade (see below). For HIV testing, all eligible girls (estimated to be an average of 100 girls per school) in up to 18 schools is large enough to detect a significant difference in testing uptake if setting statistical significance at $\alpha=0.05$, $\beta=0.2$, ICC=0.1, and an expected testing uptake of 60% (control) and 80% (intervention).

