Cluster randomized controlled trial: We will select up to 18 (2 pilot + 16 for full implementation) schools from the Urban District of Lusaka to receive the SKILLZ-Girl curriculum. Of the total (up to 18), half will be randomly allocated to host the standard SKILLZ-Girl curriculum, and the remaining half (e.g., up to eight) will be randomized to either enhanced SKILLZ-Club. Those schools randomized to standard SKILLZ Girl curriculum will only have access to SOC clubs. Those schools selected for enhanced SKILLZ Girl curriculum will offer SKILLZ Club. See **Figure 3** for study allocation flow.

Figure 3. School Selection Flow Chart

[figure not shown]
ONGOING REFERRAL TO COMMUNITY CARE FOR SERVICES

We anticipate that most of our evaluation cohort will not be HIV-infected. Thus, the retention to SRH analysis drives the sample size calculation of 351 girls using contraception at the end of two years, with, and risk ratio difference of 0.3 (30%) between the SOC and enhanced SKILLZ-Club schools. To realize the 351 needed to meet requirements for estimate sensitivity, we augment the initial sample size receiving the SKILLZ-Girl curriculum accounting conservatively for 25% uptake of SRH methods and multiplying by two to assess the difference within each SKILLZ-Girl model (phase 1) and accounting for attrition across the two years of follow-up (12.5%) resulting in a starting sample size of 3159 $((351/0.25) \times 2) \times 1.025$. **SKILLZ-CLUBS** will act as an extension to the SKILLZ-Girl curriculum enabling participants to seamlessly transition from the SKILLZ-Girl curriculum into the SKILLZ-Club. We anticipate minimal attrition (~15-20%). Participants will spend the majority of the study window in SKILLZ-Club and it is through the SKILLZ-Club affiliation that we will follow-up and ascertain outcomes for those enrolled longitudinally.

For the small minority of girls found to be HIV-infected across all schools where the study will be conducted, we will evaluate linkage to care and on treatment, VLS, and retention in care for a period of two years. These girls will be encouraged to continue on to the HIV positive-specific SKILLZ-Plus facility-based curriculum. We will quantitatively measure the impact of SKILLZ-Plus on linkage to care and treatment, retention and viral load at 6, 12, and 24 months after diagnosis (or since participant is identified by GRS as HIV+) using SmartCare data and compare to an existing matched cohort.

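### The enrolment target of 3,159–3,200 girls does not fit 16–18 schools of about 100 girls, and the plan does not give the basis of the contraception calculation that sets it

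*Combined protocol and SAP*

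**What the plan says.** **The target.** Section 8c states that "the retention to SRH analysis drives the sample size calculation of 351 girls using contraception at the end of two years". It divides 351 by an uptake of 25%, continues by "multiplying by two to assess the difference within each SKILLZ-Girl model (phase 1", and ends "accounting for attrition across the two years of follow-up (12.5%) resulting in a starting sample size of 3159". The printed formula shows a final factor of 1.025. A few lines later, after the sentence on the clubs, it adds "We anticipate minimal attrition (~15-20"%. Section 8d (baseline survey) gives a target of 3,200 girls.

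**The supply.** Section 8c also says "We will select up to 18 (2 pilot + 16 for full implementation) schools from the Urban District of Lusaka", and describes the pool as "all eligible girls (estimated to be an average of 100 girls per school) in up to 18 schools". Section 7 (Aim 1) "compares girls aged 16 and over in 9 SKILLZ control schools compared to 9 schools where enhanced SKILLZ will be delivered", and Section 8a gives up to 9 schools per arm. In Section 8c the enhanced half is put at up to eight schools. Section 4, where the two school categories are set out, instead gives up to 16 schools in each arm.

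**Clustering.** Section 8a says "Participants will be clustered at the school-level; we will enroll all girls aged 16-years at the commencement of SKILLZ-Girl". Section 8c uses an ICC of 0.1 for HIV testing, and Section 8f plans a GEE analysis by school. No ICC is given for contraception.

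**Status of the outcomes.** Section 8f names HIV testing as the primary outcome. The end of Section 4 also counts contraceptive use among the primary outcomes.

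**The concern.** The analysis said to drive the trial's size asks for nearly twice as many girls as the described schools hold. Because all eligible girls are already taken, harder recruitment cannot close the gap, and the school counts are ceilings. The one section whose school count fits the target disagrees with the others, and the text does not say which is current.

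At stake is whether a cohort of about 1,800 counts as full enrolment or as a 43% shortfall against 3,159, and what contraceptive difference the trial can detect. HIV-testing power rests on the same unsettled school count.

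**Working it through.** **1. Reproduce the plan's figure.** Inputs from Section 8c: 351 users, 25% uptake, a factor of 2, 12.5% attrition.

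- 351 / 0.25 = 1,404; × 2 = 2,808; × 1.125 = 3,159. This matches exactly.
- With the printed factor, 2,808 × 1.025 = 2,878, which does not match.
- Without the doubling, 1,404 × 1.125 = 1,580, close to 16 × 100.

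Uptake, doubling and attrition account for the whole step from 351 to 3,159, so no clustering allowance is visible there.

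**2. Supply.** Girls = schools × 100. Users at two years by the plan's own convention = girls / 1.125 × 0.25.

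| Schools | Girls | Share of 3,159 | Users, total | Users per group |
|---|---|---|---|---|
| 16 | 1,600 | 50.6% | 355.6 | 177.8 |
| 18 | 1,800 | 57.0% | 400.0 | 200.0 |
| 32 | 3,200 | 101.3% | 711.1 | 355.6 |

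Reaching 3,159 would need 3,159 / 18 = 176 or 3,159 / 16 = 197 eligible girls per school. If 12.5% loss is applied as × 0.875 instead, 16 and 18 schools give 350 and 394 users in total (175 and 197 per group).

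**3. The two readings of 351.**

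- *Per group:* 16–18 schools give 178–200 against 351, before any clustering.
- *Total:* they give 356–400 against 351. Users per school m = 100 / 1.125 × 0.25 = 22.2. The ICC that uses up the margin is (users / 351 − 1) / (m − 1): (355.6 / 351 − 1) / 21.2 = 0.0006 for 16 schools and (400 / 351 − 1) / 21.2 = 0.0066 for 18. This assumes an analysis of users only and no allowance already inside 351. For orientation, an assumed ICC of 0.01 gives a design effect of 1 + 21.2 × 0.01 = 1.21.

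**4. Could 351 already contain a clustering allowance?** The plan gives no control rate, alpha, power or ICC for contraception. Assume a 30% relative change, two-sided 5% and 80% power. Then about 351 per arm arises without clustering at a control rate near 0.31–0.35, and with a design effect of 3.1 at a control rate near 0.58–0.62. The text does not tell these apart.

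**5. HIV testing.** Inputs from Section 8c: 60% against 80%, ICC 0.1, 100 girls per school, alpha 0.05 (taken as two-sided). Design effect = 1 + 99 × 0.1 = 10.9. SE = √[(0.24 + 0.16) × 10.9 / (100c)] for c schools per arm: 0.0696 for c = 9 and 0.0738 for c = 8.

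| Schools per arm | Normal, unpooled | Normal, pooled | Noncentral t, 2c − 2 df |
|---|---|---|---|
| 9 | 82.0% | 80.7% | 77.0% |
| 8 | 77.3% | 75.8% | 71.2% |

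These figures assume equal school sizes and do not model the difference-in-difference estimator with covariates in Section 8f.

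**The case against.** The best defence is that 351 is a total and the doubling is a leftover. The wording of that step points to a comparison inside each of two curriculum models. In the design as written, each model has only one club type, so no such comparison exists. Drop the doubling and the formula gives 1,580, which fits 16 schools. This is inference, but it is at least as natural as reading 351 as per group. It stands as a reason not to say outright that 16–18 schools fail to deliver the contraception precision. It does not rescue the plan, because 3,159 and 3,200 would then be the wrong targets.

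A reader might also infer that clustering was ignored for contraception. The documents do not support that: the steps after 351 contain no allowance, but 351 itself is unexplained. The GEE analysis in Section 8f handles clustering in estimation and does not replace an allowance in the sample size.

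Nor do the documents show that HIV testing is underpowered at 18 schools. The stated 80% is met by normal approximation, and the lower figure comes from a test the plan does not name.

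Two smaller points deserve the benefit of the doubt. The 1.025 may be a text-extraction error, and the 15–20% attrition may mean drop-out from the clubs and not loss of outcome data.

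**Conclusion.** The enrolment figures conflict as written. The target is 3,159–3,200 girls, while 16–18 schools at the plan's own average of 100 supply about 1,600–1,800, or 51–57% of 3,159. Only Section 4's 32 schools fit the target, and they contradict Sections 7, 8a and 8c. This rests on the protocol's own numbers. Two figures are missing from the available text, but they could not remove a conflict within the text.

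The consequence for contraception is conditional. If 351 is per group, about half the required users are available (178–200 against 351). If it is a total, 16–18 schools meet it only if any further ICC stays at or below about 0.001 (16 schools) or 0.007 (18). A shortfall in contraception precision is therefore certain only on the per-group reading.

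HIV-testing power is in line with the plan at 9 schools per arm by normal approximation and falls to about 71–77% at 8. Whether the two pilot schools are analysed therefore decides whether the stated power is met.

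**What to change.** 1. Reconcile Sections 4, 7, 8a, 8c and 8d to one school count, one girls-per-school figure and one enrolment target. The choice is the sponsor's.
2. If the design is 16–18 schools of about 100 girls, replace 3,159 and 3,200 with the 1,600–1,800 that will be enrolled. Restate the contraceptive difference this number can detect, with a school-level design effect 1 + (m − 1) × ICC, where m matches the analysis population.
3. State whether 351 is per group or a total, what the doubling represents, and the control rate, alpha, power and ICC behind it. Define the risk ratio difference of 0.3.
4. Verify the 1.025 factor against the source file, and say which attrition figure applies to outcome loss.
5. Say whether the two pilot schools are analysed. Restate HIV-testing power for the resulting school count, naming the test.

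Cost: rewording and recalculation if 16–18 schools is the design. If the sponsor confirms 3,200 girls or 16 schools per arm, the school or recruitment plan in Sections 7 to 8c has to change. The downside is that the stated contraception precision, and possibly the testing power, will look less favourable.

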Cultural factors, such as the widespread belief in Zambia that a girl or woman should not say no to sex or propose the use of a condom, have obvious consequences to a poor understanding and access to SRH services.⁴⁴ These barriers to accessing services and adhering to risk reduction strategies exist across all levels of influence: individuals may hold fears and misconceptions of HIV and suffer from stigma surrounding adolescent sexuality; fears and anxiety can lead to a lack of social support from partners and peer groups that would otherwise be protective; families and communities are often the source of perceived stigma, and further reinforce inequitable gender and social norms that amplify girls' vulnerability; health systems are often inaccessible and unfriendly to young people.³¹⁻³³ These myriad factors collide to prevent adolescent girls from reducing risk, accessing HIV and SRH services, and remain in care over the longer-term.

There is however increasing access to cost-effective and easy to use long-acting methods of contraception such as the 3-month intramuscular administered depo medroxyprogesterone acetate (DMPA-SC). This has been specifically designed to overcome some of the major barriers to contraceptive use, including difficulty in accessing facility-based SRH services. Research to date has consistently demonstrated its safety, effectiveness and acceptability to both users and health care providers^{45 46,47}. Furthermore, use of a contraceptive method has been associated with an increased likelihood to be tested for HIV and a decrease in high-risk sexual behaviors⁴⁸. Unfortunately contraceptive failure and discontinuation is more common amongst adolescent girls than among older women⁴⁹ and only 20.6% of sexually active adolescent girls who reported not wanting to become pregnant reported that they were using any contraceptive method to prevent pregnancy.³ While DMPA-SC is currently being scaled up in over 22 countries around the world, including Zambia, the national strategy for Zambia does not provide specific plans for addressing the SRH needs among adolescent girls. Thus, there is an urgent need to fill this gap and identify effective strategies

for ensuring health equity whereby adolescent girls have access to the same expanded contraceptive method mix in Zambia.

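### Section 8c gives three attrition figures that do not agree, its printed formula does not give 3,159, and no term covers girls who stop a method

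*Combined protocol and SAP*

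**What the plan says.** The calculation is in Section 8c (*Selection of participants, sampling methods and sample size*), in the paragraph after Figure 3. It says that "the retention to SRH analysis drives the sample size calculation of 351 girls using contraception at the end of two years", with an effect described as a "risk ratio difference of 0.3 (30%) between the SOC and enhanced SKILLZ-Club schools".

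The starting number is then built in three steps:

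- "accounting conservatively for 25% uptake of SRH methods";
- "multiplying by two to assess the difference within each SKILLZ-Girl model (phase 1");
- "accounting for attrition across the two years of follow-up (12.5%) resulting in a starting sample size of 3159".

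The formula printed beside the result divides 351 by 0.25, doubles, and multiplies by 1.025.

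Two sentences later, just after describing the passage of girls from SKILLZ-Girl into SKILLZ-Club, the section adds: "We anticipate minimal attrition (~15-20" per cent). The next sentence makes Club membership the route for longitudinal follow-up and outcome ascertainment.

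Three other places bear on this:

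- Section 8d, baseline survey: the target sample is 3,200 girls.
- Section 8d, follow-up surveys: girls who miss the Club, leave or change school are to be traced in the community, and schools without SKILLZ-Club hold a separate survey session.
- Section 5: "contraceptive failure and discontinuation is more common amongst adolescent girls than among older women". No rate is given.

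**The concern.** One paragraph carries three loss figures: 12.5% in words, 2.5% implied by the printed factor, and about 15-20% expected. They cannot all describe loss of the two-year outcome, and the printed formula does not produce the printed answer. Inflating by multiplication also gives less protection than the stated 12.5%.

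The target is defined as "351 girls using contraception at the end of two years", which is a measure of continued use. The only factors that reduce the cohort to that number are uptake and study attrition. A girl who starts a method and stops it, but stays in the study, is counted as a user.

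At stake is whether the number that the section says drives the sample size follows from its own inputs, and how many two-year users, and so what precision, the contraceptive comparison can be expected to have.

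**Working it through.** **Inputs, all from Section 8c unless noted:** 351 users at two years; 25% uptake; doubling; 12.5% attrition in words; 1.025 in the formula; about 15-20% expected attrition; 3,200 survey target (Section 8d). No control rate, alpha, power or ICC is attached to the 351, so that figure cannot be reproduced. The alpha, beta and ICC that Section 8c does give are for HIV testing.

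**1. The plan's own figure**

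- Base: (351 / 0.25) x 2 = 2,808
- Formula as printed: 2,808 x 1.025 = 2,878
- With 12.5% added on: 2,808 x 1.125 = 3,159, an exact match

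So 3,159 was obtained with 1.125.

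**2. What multiplying by 1.125 protects against**

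1 - 1/1.125 = 11.1%. This is below both rates that the paragraph states in words.

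**3. Starting number with division by (1 - loss)**

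- 12.5%: 2,808 / 0.875 = 3,209.1, so 3,210
- 15%: 2,808 / 0.85 = 3,303.5, so 3,304
- 20%: 2,808 / 0.80 = 3,510

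At 12.5% the gap is 3,210 - 3,159 = 51 girls, or 1.6%.

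**4. Users delivered if 351 is needed in each half** (N x (1 - loss) x 0.25 / 2, nobody stopping)

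| Loss | From 3,159 | Short of 351 | From 3,200 |
|---|---|---|---|
| 12.5% | 345.5 | 1.6% | 350 |
| 15% | 335.6 | 4.4% | 340 |
| 20% | 315.9 | 10.0% | 320 |

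**5. Users delivered if 351 is the total** (N x (1 - loss) x 0.25, N = 3,159)

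| Loss | Users | Share who must stop before the total falls below 351 |
|---|---|---|
| 12.5% | 691 | 1 - 351/691.0 = 49% |
| 15% | 671 | 1 - 351/671.3 = 48% |
| 20% | 632 | 1 - 351/631.8 = 44% |

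**6. Stopping a method**

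On the per-half reading, 3,159 x 0.25 / 2 = 394.9 starters. Since 351/394.9 = 0.889, any combined loss from attrition and stopping above 11.1% misses the target. No continuation rate is needed to see this.

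As an illustration only, because the documents give no rate: if 10-30% of retained users stopped, the per-half yield would be 311-242 at 12.5% attrition (345.5 x 0.9 and x 0.7) and 284-221 at 20% (315.9 x 0.9 and x 0.7).

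**The case against.** The sponsor has several good answers.

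- **The 1.025 is almost certainly a misprint.** Only 12.5% produced 3,159, and the misprint did not shrink the sample. A reader might infer that the cohort was sized for 2.5% loss; the exact match at 1.125 rules that out. This stands.
- **Multiplying instead of dividing matters little.** It costs 51 girls, and the 3,200 target gives 350 users per half at 12.5% loss. This stands at 12.5%, but 3,200 does not close the gap at 15-20%.
- **The 15-20% may describe Club attendance.** SKILLZ-Club exists only in the enhanced arm, and Section 8d provides for tracing and for a separate survey session in the other schools. A reader might take 15-20% as the loss of two-year outcomes in both arms; the documents do not support that as fact. Yet Section 8c itself says that outcomes are ascertained through Club affiliation, and nowhere links the tracing to 12.5%. So the rates need reconciling, and 336 and 316 are conditional figures.
- **The 351 may be a total.** A reader might conclude outright that 3,159 girls fail to yield 351 users. That needs 351 in each half. The doubling points that way, since it would otherwise serve no clear purpose, but it is explained by SKILLZ-Girl model, and in the current design Club type follows that model one to one. The text does not settle it.
- **The 25% is called conservative and could be meant as use at 24 months.** If so, no continuation term is needed. The wording speaks of uptake, so this has to be stated.
- **Recruitment would not change.** The plan enrols all eligible girls in the chosen schools, and HIV testing, the primary outcome in Section 8f, has its own justification. This stands and limits the importance of the point.

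**Conclusion.** The point holds as an inconsistency in the sample-size paragraph. The printed formula gives 2,878. The figure 3,159 rests on 1.125, which offsets 11.1% loss and so falls short of the paragraph's own 12.5% and 15-20%. No term covers stopping a method, although the target is use at two years.

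The consequence depends on what 351 means. If it is per half, the shortfall from attrition alone is 1.6% at 12.5% loss, 4.4% at 15% and 10.0% at 20%, and any stopping adds to it. If it is the total, 3,159 is sufficient unless about 44-49% of users stop. Both statements take 25% as uptake and apply one loss rate to all girls. How much stopping would reduce the yield cannot be derived from the documents, and a claim that a particular share of starters will have stopped would have no source in them.

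The primary HIV-testing comparison is not affected. These figures take 3,159 as given; whether the schools can supply that many girls is a separate question.

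**What to change.** Rewrite the sample-size paragraph in Section 8c, without enrolling more girls:

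1. Correct the factor 1.025.
2. Reconcile 12.5% with 15-20% into one justified rate of two-year outcome loss, taking account of the tracing and survey sessions in Section 8d, and divide by (1 - loss).
3. State whether 351 is needed in each half or in total, and what the doubling is for.
4. State whether 25% means ever taking up a method or using one at 24 months. If uptake, add a justified continuation rate.
5. Restate the number of two-year users that the sample delivers, and the detectable difference. The sponsor must supply the control rate, alpha, power and ICC behind 351.

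The cost is one reworded paragraph plus the missing design inputs. The stated precision may become somewhat less favourable; no participants are added.
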